6.5.3 Dose modifications

For subjects who do not tolerate the protocol-specified dosing schedule, dose interruptions (for MBG453, azacitidine and venetoclax), and/or dose reductions (azacitidine and venetoclax only) are either recommended or mandated in order to allow subjects to continue the study treatment.

Guidelines for permanent treatment discontinuation is mandatory for specific events indicated as such in [Table 6-5](#) and [Table 6-6](#).

Dose interruption at the start of a new treatment cycle

In subjects who have achieved CR, CRI or MLFS and have Grade 4 neutropenia and/or Grade 4 thrombocytopenia lasting at least 7 days dosing of both venetoclax and azacitidine should be interrupted until resolution to \leq Grade 2 or to a clinically significant threshold per investigator assessment ([NCCN 2021](#)). In case of a prolonged cytopenia, close blood monitoring is required, and the investigator should consider repeating bone marrow examination to determine if morphologic remission (CR, CRI, MLFS) is ongoing. Administer growth factors if indicated ([NCCN 2021](#)). MBG453 should not be administered during the dose interruption. After resolution, dosing of both azacitidine and venetoclax should be resumed on the same day with dose modification for venetoclax as specified in [Table 6-6](#). The first day dosing is resumed will be considered as D1 of the new treatment cycle and MBG453 will be administered on Day 8 of the new cycle. In cases in which venetoclax and azacitidine have been permanently discontinued and the patient remains on MBG453, then in subjects who have achieved CR, CRI or MLFS and have Grade 4 neutropenia and/or Grade 4 thrombocytopenia dosing of MBG453 should be interrupted until resolution to \leq Grade 2. The first day dosing with MBG453 is resumed will be considered D8 of the new cycle.

Dose modifications for MBG453

Dose modifications for MBG453 will be done according to ASCO guidelines about management of immune-related AEs ([Schneider et al 2021](#)).

Additionally, the guidance indicated in [Table 6-5](#) below, provides instructions for infusion reaction, immune-related adverse events not covered by ASCO guidelines and a general guideline for non-hematologic non-immune-related toxicities that are clinically significant per investigator judgement and possibly attributable to the investigational drug. This general guideline will not apply in case of non-hematologic non-immune-related toxicities that are attributable to azacitidine, venetoclax and AML and its complications.

Deviations to dose interruptions, reductions and/or permanent discontinuations outlined in [Table 6-5](#) are not allowed.

Administration of MBG453 may be delayed due to toxicities. A scheduled dose may be delayed within a cycle by up to 14 days. If a dose cannot be administered within the planned window within the cycle, then the dose should be skipped. Next scheduled dosing may resume once the adverse event has resolved to \leq Grade 1 or baseline per the next planned treatment cycle. Dose reductions for MBG453 are not allowed.

Overall, for adverse events of potential immune-related etiology (irAE) that do not recover to \leq Grade 1 or baseline at a dose of immunosuppression of \leq 10 mg/day prednisone or equivalent (or as indicated in [Table 6-5](#)) within 12 weeks after initiation of immunosuppressive therapy, MBG453 must be permanently discontinued.

Table 6-5 Criteria for dose interruption and re-initiation of study drug MBG453 for adverse drug reactions

Worst Toxicity Grade (CTCAE v5.0)	Recommended Dose Modifications
Infusion Reaction	
Grade 1	Decrease infusion rate until recovery
Grade 2	
Stop infusion
 
Before restarting - pre-medicate according to local institutional guidelines.
 
Restart infusion at 50% of previous rate under continuous observation. Ensure that there is a minimum observation period of 1 hour prior to restarting the infusion(s). If the AE recurs at the reinitiated slow rate of infusion, and despite oral pre-medication*, then discontinue MBG453

Grade 3	
Stop infusion
 
If the AE resolves to \leq Grade 1 within 72hrs:
 
 At next scheduled treatment visit, pre-medicate according to local institutional guidelines. Restart infusion at 50% of previous rate under continuous observation. Ensure that there is a minimum observation period of 1 hour. If the AE recurs despite slow rate of infusion and pre-medication*, then discontinue MBG453 
If the AE does not resolve to \leq Grade 1 within 72hrs:
 
 Discontinue MBG453

Worst Toxicity Grade (CTCAE v5.0)	Recommended Dose Modifications
Grade 4	Discontinue MBG453
For adverse events thought to be immune-related AEs and not covered in the ASCO Guidelines for the management of immune-related adverse events in subjects treated with immune checkpoint inhibitor therapy (Schneider et al 2021)	
Grade 1	Continue treatment with MBG453
Grade 2 or Grade 3 ≤ 7 days	Delay treatment with MBG453 until resolved to ≤ Grade 1 or baseline
Grade 3 lasting > 7 days but < 21 days	1st and 2nd occurrence Delay study treatment until resolved to ≤ Grade 1 or baseline 3rd occurrence: Discontinue study treatment
Grade 3 lasting ≥ 21 days Or Grade 4	Discontinue study treatment
Dermatological toxicities	
Grade 1	Maintain MBG453. Use topical steroids, antihistamines, topical emollients.
Grade 2	Consider interrupting MBG453. Use topical or oral steroids, antihistamines. If MBG453 is interrupted and resolution to ≤ Grade 1, restart MBG453.
Grade 3 or 4	Interrupt MBG453. Manage per institutional practice. After resolution to ≤ Grade 1, consider restarting MBG453.
Bullous dermatitis	Grade 1, 2 and 3: Interrupt MBG453. Consult with dermatologist for appropriateness to restart MBG453. Grade 4: Permanently discontinue MBG453.
Stevens-Johnson syndrome (SJS), or Lyell syndrome/toxic epidermal necrolysis (TEN)	Permanently discontinue MBG453.
For non-hematological, non immune related toxicities clinically significant** and possible attributable to the investigational drug (NCI CTCAE v5.0)	
(The guideline does not apply to for toxicities attributable to azacitidine or venetoclax or the underlying AML including its complications)	
Grade 1 and Grade 2 tolerable	Continue treatment with MBG453
Grade 2 intolerable (includes all Grade 2 events defined as DLT in Table 6-4) and Grade 3	1st or 2nd occurrence: 
Interrupt MBG453 until toxicity recovers to ≤ Grade 1 or baseline
Once recovered to ≤ Grade 1 or baseline restart MBG453 at the same dose level and schedule AE resolution to ≤ Grade 1 or baseline must occur within a maximum period of 56 days since interruption, otherwise MBG453 must be permanently discontinued. 3rd occurrence: 
Permanently discontinue MBG453
Grade 4	Discontinue MBG453

Worst Toxicity Grade (CTCAE v5.0)	Recommended Dose Modifications
All dose modifications should be based on the available information and worst preceding toxicity	
*Prophylaxis regimens will include both paracetamol/acetaminophen and an antihistamine.	
**Per investigator judgement	

Dose modifications for azacitidine

If azacitidine treatment is deemed by the investigator to possibly have contributed to an observed adverse event, the dose or schedule of azacitidine treatment may be modified within a cycle and/or for subsequent cycles or temporary/permanent interruptions of azacitidine treatment may be decided by the investigator according to local practice and/or the country-specific label guiding azacitidine use.

Dose modifications for venetoclax

If venetoclax treatment is deemed by the investigator to possibly have contributed to an observed adverse event, the dose or duration of venetoclax treatment may be modified according to the following guidelines:

Table 6-6 Dose modifications for venetoclax

Event	Occurrence	Action
Grade 4 neutropenia with or without fever or infection; or Grade 4 thrombocytopenia	Occurrence prior to achieving remission (CR, CRi, MLFS)	Transfuse blood products, administer prophylactic and treatment anti-infectives as clinically indicated.
	First occurrence after achieving remission (CR, CRi, MLFS) and lasting at least 7 days	Delay subsequent treatment and monitor blood counts. Administer granulocyte-colony stimulating factor (G-CSF) if clinically indicated for neutropenia. Once the toxicity has resolved to Grade 1 or 2, resume venetoclax therapy at the same dose
	Subsequent occurrences in next treatment cycles after achieving remission (CR, CRi, MLFS) and lasting at least 7 days	Delay subsequent treatment and monitor blood counts. Administer G-CSF if clinically indicated for neutropenia. Once the toxicity has resolved to Grade 1 or 2, resume venetoclax therapy at the same dose with a duration reduced by 7 days for each subsequent treatment cycle
Blood chemistry changes suggestive of TLS	-	Withhold treatment. If the event is resolved within 48 hours of last dose, treatment with venetoclax can be resumed at the same dose.

Event	Occurrence	Action
Events of clinical TLS or blood chemistry changes requiring more than 48 hours to resolve	-	Withhold treatment. Treatment should be resumed at a reduced dose (per the investigator discretion). When resuming treatment after interruption due to TLS, the instructions for prevention of TLS should be followed.
Grade 3 or 4 non-hematologic toxicities	First occurrence	Withhold treatment. Once the toxicity has resolved to Grade 1 or baseline level, venetoclax therapy may be resumed at the same dose.
	Subsequent occurrences	Withhold treatment. Treatment should be resumed at a reduced dose (per the investigator discretion).

Permanent discontinuation of study treatment

If the study treatment (i.e. MBG453 + azacitidine + venetoclax) is interrupted for toxicities and the start of the subsequent study treatment cycle is delayed for more than 42 consecutive days (measured from the intended start date of the new cycle (Day 29 of the previous cycle) in absence of clinical benefit for the patient per investigator assessment, the subject should be discontinued from study treatment.

At any time during the study, patients unable to tolerate one or two of the study treatment drugs may continue study treatment with only the tolerated drug(s) provided the subject benefits per investigator's judgement.

These dose changes must be recorded on the appropriate CRF.

6.5.4 Follow-up for toxicities

Subjects whose treatment is interrupted or permanently discontinued due to an AE or clinically significant laboratory value, must be followed-up at least once a week (or more frequently if required by institutional practices, or if clinically indicated) for 4 weeks, and subsequently at approximately 4-week intervals, until resolution or stabilization of the event, whichever comes first. Appropriate clinical experts should be consulted as deemed necessary.

All subjects must be followed up for AEs (including irAEs and SAEs) for 30 days following the last dose of venetoclax or azacitidine (whichever was later) and 150 days following the last dose of MBG453, whichever is later.

6.5.4.1 Follow-up for immune-related AEs

The emergence of Immune-Related AE (irAE) may be anticipated based on general experience in clinical studies with similar class of compounds that block the negative immune regulators.

An irAE is any clinically significant AE affecting any organ that is associated with study drug exposure, is consistent with an immune-mediated mechanism, and where alternative explanations have been investigated and ruled out or are considered to be unlikely. Serologic,

histologic and immunological assessments should be performed as deemed appropriate by the Investigator, to verify the immune related nature of the AE. An empiric trial of corticosteroids may also contribute to understanding the etiology of a potential irAE. All subjects with signs or symptoms of irAEs should be monitored and managed following the ASCO Guidelines for the management of immune-related adverse events in subjects treated with immune checkpoint inhibitor therapy (Schneider et al 2021). See guidance in [Table 6-5](#) for immune-related AEs not covered by ASCO guidelines.

In case of a suspected irAE, the relevant immunological assessments (e.g. rheumatoid factor, anti-DNA Ab, etc.) should be performed. In case of a toxicity suspected to be a cytokine release syndrome, the cytokine assessments outlined in [Table 8-1](#) must be performed.

Subjects should be monitored carefully for any skin toxicity or mucositis and study treatment should be discontinued for any suspected case of SJS/TEN.

6.5.4.2 Follow-up for Tumor Lysis Syndrome (TLS)

Tumor lysis syndrome (TLS) is a clinical entity frequently observed in hematological malignancies resulting from massive tumor cells lysis. It is characterized by a constellation of metabolic abnormalities caused by the massive and abrupt release of cellular components (including nucleic acids, proteins, and electrolytes) into the systemic circulation after the rapid lysis of malignant cells (Cairo and Bishop 2004, Coiffier et al 2008).

During this study, subjects should be closely monitored (including relevant laboratory tests) for signs and symptoms of TLS before initiation and during a treatment cycle.

To minimize risk of TLS, all subjects should receive allopurinol, or an alternative prophylaxis with anti-hyperuricemic agents, as well as adequate hydration (including instructing patients to drink 1.5 to 2.0 L of water daily, among other measures as clinically indicated), prior to study treatment. Events should be managed according to local guidelines. Also see [Section 8.4.4](#) for considerations during the venetoclax ramp-up.

Before initiation of a treatment cycle and during a treatment cycle, the following measures should be followed:

- **Before initiation of a treatment cycle**

- Prophylactic allopurinol, or a non-allopurinol alternative (eg, febuxostat), and increased oral/ i.v. hydration prior to treatment should be given in subjects with elevated uric acid or high tumor burden
- Prompt supportive care in case of acute TLS (i.v. fluids and treatment with rasburicase as clinically indicated, when uric acid continues to rise despite allopurinol/febuxostat and fluids)

- **During a treatment cycle**

- Frequent monitoring of the following laboratory tests (per assessment cycle and as clinically indicated): potassium, phosphorus, calcium, creatinine, and uric acid
- Encourage oral hydration

Based on laboratory and clinical TLS criteria (modified from [Cairo and Bishop 2004](#)), the following measures for TLS should be also followed:

Laboratory tumor lysis syndrome

- Defined as two or more of the following values within three days before or in the days following initiation of a treatment cycle:
 - Uric acid ≥ 8 mg/dL or 25% increase from baseline
 - Potassium ≥ 6 mEq/L or 25% increase from baseline
 - Phosphorus ≥ 6.5 mg/dL (children) or ≥ 4.5 mg/dL (adults) or 25% increase from baseline
 - Calcium ≤ 7 mg/dL or 25% decrease from baseline
- Regimen:
 - If none or one of the laboratory values above is abnormal, continue to manage with allopurinol or a non-allopurinol alternative (e.g., febuxostat) and oral fluids. If uric acid remains elevated, consider i.v. fluids, treatment with rasburicase, and hospital monitoring.
 - Laboratory TLS should be managed with i.v. fluids, laboratory blood tests every 6 to 8 hours and inpatient care. Cardiac monitoring and treatment with rasburicase should be considered if uric acid remains elevated.

Clinical tumor lysis syndrome

- Defined as the presence of laboratory TLS and ≥ 1 of the following criteria that cannot be explained by other causes:
 - Serum creatinine ≥ 1.5 times the upper limit of the age-adjusted normal range
 - Symptomatic hypocalcemia
 - Cardiac arrhythmia
- Regimen:
 - Clinical TLS should be managed with i.v. fluids, laboratory blood tests every 6 to 8 hours, cardiac monitoring, treatment with rasburicase/allopurinol/febuxostat and inpatient care (consider intensive care unit (ICU)).

Subjects who have been treated for TLS with favorable outcome (defined as return to within 10% of baseline value or within limit of normal of relevant laboratory parameters) may re-start study treatment upon investigator's discretion.

6.5.4.3 Follow up on potential drug-induced liver injury (DILI) cases

Guidelines for follow-up on potential DILI cases are described in [Table 6-7](#) and [Table 6-8](#).

Table 6-7 Follow-up of abnormal liver chemistry results

ALT	TBL	Liver Symptoms	Action
ALT increase without bilirubin increase:			
If normal at baseline:	Normal	None	
 • No change to study treatment
ALT $> 3 \times$ ULN			
If elevated at baseline:			

ALT	TBL	Liver Symptoms	Action
ALT > 2 x baseline or > 200 U/L (whichever occurs first)	For patients with Gilbert's syndrome: No change in baseline TBL		
 Measure ALT, AST, ALP, GGT, TBIL, INR, albumin, CK, and GLDH in 48-72 hours. Follow-up for symptoms
If normal at baseline: ALT > 5 x ULN for more than two weeks	Normal For patients with Gilbert's syndrome: No change in baseline TBL	None	
 Interrupt study drug Measure ALT, AST, ALP, GGT, TBIL, INR, albumin, CK, and GLDH in 48-72 hours. Follow-up for symptoms.
If elevated at baseline: ALT > 3 x baseline or > 300 U/L (whichever occurs first) for more than two weeks			
 Initiate close monitoring and workup for competing etiologies.
If normal at baseline: ALT > 8 x ULN	Normal	None	
ALT increase with bilirubin increase:			
If normal at baseline: ALT > 3 x ULN	TBL > 2 x ULN (or INR > 1.5)	None	
If elevated at baseline: ALT > 2 x baseline or > 200 U/L (whichever occurs first)	For patients with Gilbert's syndrome: Doubling of direct bilirubin		
 Study drug can be restarted only if another etiology is identified and liver enzymes return to baseline.
If normal at baseline: ALT > 3 x ULN	Normal or elevated	Severe fatigue, nausea, vomiting, right upper quadrant pain	
If elevated at baseline: ALT > 2 x baseline or > 200 U/L (whichever occurs first)			

Table 6-8 Action required for isolated total bilirubin elevation

Abnormality	Action required
Any elevation > ULN	Fractionate bilirubin, evaluate for cholestatic liver injury (ALP) or alternative causes of bilirubin elevation. Treat alternative causes according to local institutional guidelines
Grade 2 (>1.5 - 3.0 ULN)	Maintain treatment. Repeat LFTs within 48-72 hours, then monitor LFTs weekly until resolution to ≤ Grade 1 or to baseline
Grade 3 (>3.0 – 10 ULN)	Interrupt treatment. Repeat LFTs within 48-72 hours, then monitor LFTs weekly until resolution to ≤ Grade 1 or to baseline
Grade 4 (> 10 x ULN)	Discontinue study treatment

If abnormalities are confirmed, close observation and follow-up are required:

1. A detailed history, including relevant information, such as cardiac disease, history of any pre-existing liver conditions or risk factors, blood transfusions, i.v. drug abuse, travel, work, alcohol intake, and full clinical examination for evidence of acute or chronic liver disease, cardiac disease and infection etc. should be performed.
2. Review of concomitant medications, including nonprescription medications and herbal and dietary supplement preparations, alcohol use, recreational drug use, special diets, and chemicals exposed to within one month of the onset of the liver injury.
3. Further testing for acute hepatitis A, B, C or E infection and liver imaging (e.g. biliary tract) may be warranted.
4. Obtain an unscheduled PK sample, as close as possible to last dose of study treatment.

Additional testing for other hepatotropic viral infection (CMV, EBV or HSV), autoimmune hepatitis or liver biopsy may be considered as clinically indicated or after consultation with specialist/hepatologist.

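### Tables 6-5 and 6-7 give opposite restart instructions for MBG453 after a narrow class of unexplained liver events, and the protocol does not say which table governs

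*Protocol*

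**What the plan says.** **Table 6-5 (Protocol Section 6.5.3).** One block covers non-hematological, non-immune toxicity that is clinically significant and "possible attributable to the investigational drug". The row at issue is "Grade 2 intolerable (includes all Grade 2 events defined as DLT in Table 6-4) and Grade 3". At a first or second occurrence MBG453 is interrupted; on recovery to Grade 1 or lower, or to baseline, the site is told to "restart MBG453 at the same dose level and schedule". Recovery "must occur within a maximum period of 56 days since interruption, otherwise MBG453 must be permanently discontinued". A third occurrence, or Grade 4, means discontinuation. The section states one exclusion: "This general guideline will not apply in case of non-hematologic non-immune-related toxicities that are attributable to azacitidine, venetoclax and AML and its complications".

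**Table 6-4 (Section 6.5.2).** The liver DLT is bilirubin of Grade 2 or higher together with ALT and/or AST of Grade 2 or higher.

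**Table 6-7 (Section 6.5.4.3).** The ALT-with-bilirubin block starts, for a patient with normal baseline ALT, at ALT above 3 x ULN with total bilirubin above 2 x ULN or INR above 1.5. Its restart rule is: "Study drug can be restarted only if another etiology is identified and liver enzymes return to baseline".

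**Table 6-8 (same section).** Bilirubin above 1.5 to 3.0 x ULN is Grade 2, above 3.0 to 10 is Grade 3, and above 10 is Grade 4.

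**The concern.** The Table 6-5 row asks only whether the event has recovered in time. Table 6-7 also asks whether something else caused it. When the work-up finds nothing else, suspicion of MBG453 is at its highest, and that is where the two instructions part.

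A site following Table 6-5 literally would give MBG453 again, at full dose, after unexplained combined ALT and bilirubin injury. It could do so twice in one patient (first and second occurrence). Table 6-7 would allow none. The stake is patient safety and uniform handling across sites, not the estimate of the CR rate.

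**Working it through.** There is no planned figure to reproduce. The check sets the rules side by side and asks which events meet both.

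**1. Does Table 6-7 cover MBG453?** Yes. Section 6.1 calls MBG453 the Novartis study drug, and the title of Table 6-5 uses the same term for it.

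**2. Are liver events carved out of Table 6-5?** No. The stated exclusion concerns attribution to azacitidine, venetoclax or AML. Table 6-5 in fact reaches combined liver events, because its Grade 2 row points to the DLTs of Table 6-4.

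**3. Where do the tables overlap when no other cause is found?** The ALT condition of Table 6-7 is taken as met throughout, at a first or second occurrence recovering within 56 days.

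| Event | Table 6-5 | Table 6-7 |
|---|---|---|
| Bilirubin >3.0 to 10 x ULN (Grade 3), ALT/AST below Grade 4 | Restart, same dose | No restart |
| Bilirubin >2 to 3.0 x ULN (Grade 2), ALT/AST Grade 2 or 3 | Restart, same dose (Grade 2 liver DLT, or worst grade 3) | No restart |
| Bilirubin >10 x ULN (Grade 4) | Discontinue | No restart |
| ALT or AST Grade 4, any bilirubin | Discontinue | No restart |

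The first two lines conflict. The last two do not, because the Table 6-5 footnote says "All dose modifications should be based on the available information and worst preceding toxicity", so a Grade 4 value in any liver test sets the action. The table illustrates the overlap through the bilirubin limb only. It does not cover the INR limb or the symptomatic row, and it is not a measure of how often conflict occurs.

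**4. Where does the conflict stop?** At a third occurrence, or with recovery later than 56 days, both tables lead to no restart. If another cause is found and enzymes are back at baseline, Table 6-7 permits restart and the instructions no longer oppose each other. The recovery targets differ (Grade 1 or lower, or baseline, against baseline alone) but are compatible, since reaching baseline meets both.

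**5. Is precedence stated?** No. The sentence in Section 6.5.3 forbidding deviations from Table 6-5 names interruptions, reductions and permanent discontinuations. It does not name restarts. The same section makes discontinuation mandatory for events so marked in Tables 6-5 and 6-6, without mentioning Table 6-7. Section 6.5.4.3 does not refer back to the Table 6-5 restart rule.

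**The case against.** The best counter-argument is that the protocol already signals the answer. Section 6.5.3 describes this block of Table 6-5 as a general guideline, and the table's action column is headed as recommendations. Section 6.5.4.3 is dedicated to possible drug-induced liver injury, with its own triggers, work-up and restart rule. A site that withholds MBG453 breaks no binding rule; a site that restarts breaches an express condition. This stands in large part: the liver table is the more natural one to follow. A reader might infer that the two actions are equally supported, or that one table is wrong in itself, and the documents do not bear that out. What remains is that the order has to be inferred, on a safety rule where it could simply be stated.

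Second, few events will qualify. Section 6.5.4.1 defines an immune-related event as one consistent with an immune mechanism "where alternative explanations have been investigated and ruled out or are considered to be unlikely". Finding no other cause therefore tends to move a liver event out of the non-immune row and into immune-related management. This also stands, though an unexplained event without immune features stays in the row.

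Third, there are safeguards. Section 9.1.1 requires treatment to stop where there is a safety risk, and Section 6.5.2 requires medical monitor consultation before treatment continues after a DLT. The first rests on judgement and the second is limited to the run-in observation period, so neither replaces a fixed restart rule.

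**Conclusion.** The point holds as a minor safety clarification. The conflict arises only when all of these are true: the event is clinically significant, non-immune and possibly attributable to MBG453; it meets the ALT-with-bilirubin rows of Table 6-7; its worst grade is 3, or it is a Grade 2 liver DLT; it is a first or second occurrence recovering within 56 days; and no other cause is found. In that set Table 6-5 directs up to two same-dose restarts per patient and Table 6-7 permits none.

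**Assumptions.** The protocol prints no ALT or AST grade limits. The Grade 3 bilirubin line assumes ALT/AST below Grade 4. The Grade 2 bilirubin line assumes ALT/AST at Grade 2 or 3. Using the Grade 2 DLT route outside the run-in assumes that Table 6-5 refers to the criteria in Table 6-4 and not to the observation period. The action column of Table 6-7 is broken in the text available, but the restart condition sits within the ALT-with-bilirubin block.

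**What should not be inferred.** The documents give no frequency for such events, so no claim about how many patients are affected is possible. The primary result is not at risk: Section 12.4.1 counts every CR regardless of interruption or discontinuation of study treatment. The conflict shown does not extend to isolated ALT rises or to isolated bilirubin rises under Table 6-8. The practical reach is small. All 90 subjects were enrolled by Amendment 5 (December 2022), and SAP Section 1 records that the termination letter went out on 11 January 2024. Protocol Section 9.1.4 lets benefiting patients complete treatment per protocol or elsewhere, and the documents do not say whether any remain on it.

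**What to change.** Add one sentence to the non-hematological, non-immune rows of Table 6-5:

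> *For hepatic events meeting the ALT-with-bilirubin rows of Table 6-7, the Table 6-7 restart condition governs: MBG453 may be restarted only when a different cause has been found and liver enzymes are back at baseline. The 56-day limit and third-occurrence discontinuation of this table continue to apply.*

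The closing clause matters because giving Table 6-7 precedence without it could be read as lifting the time and occurrence limits. Isolated-ALT events and Table 6-8 events should be left out of the sentence, since no conflict has been shown for them.

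The cost is one sentence, by amendment or by a clarification letter to any site with a patient still on treatment. No extra data or visits are needed. The same wording should be carried into any roll-over or other protocol that reuses these two tables.
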